### B.1. Organizational Chart

The Coordinating Unit for this Collaboratory will be situated physically and organizationally at the School of Medicine in UniAndes. The leader of this School is the Dean, [name], who is very supportive of this application. [name] is the Research Director of the School. The Coordinating Unit will lead operations in Colombia and will be assisted by a full time research assistant and the consulting experts from Stanford. The Steering Committee will guide the Coordinating Unit in decision-making and problem solving. The Steering Committee will be co-chaired by Drs. [name] and [name] (as Dual PIs), and will include the other co-investigators (Drs. [name], [name], and [name]) and a representative each from Universidad del Rosario, Fundacion Simmon, Institutes of Sports and Recreation of Bogotá, Ministry of Sports, National Institute of Cancer in Colombia, and the Colombian Obesity Foundation. The **Organization Chart** below (**Figure 1**) summarizes the infrastructure and key partnerships for the proposed S-C projects and activities.

### B.2. Modes of Operation

The Coordinating Unit will maximize efficiency of the research through its recruiting and other activities, which include providing assistance with identification of potential research subjects, coordinating meetings among research staff, facilitating subject retention throughout the studies, providing oversight of human subjects and data safety and monitoring, overseeing budgets and expenditures, and coordinating the management of staff, writing of papers, submission of ancillary studies, presentations at scientific meetings, and addressing problems in all of these areas as they occur. The Coordinating Unit also will avoid duplication of effort while assuring efficiency and coordination of all scientific activities through some of the following processes described below:

[figure not shown]
- ***In-person meetings in Colombia:*** the Coordinating Unit will plan and oversee the in-person meetings in Colombia.
- ***Teleconferences:*** The Coordinating Unit will plan and arrange at least two teleconferences per month with the research team at Stanford to update the team and solicit feedback and ideas related to research progress and findings, any problems, and results as well as on the establishment and maintenance of the multi-sectoral research network.
- ***Annual meetings of Stanford and Colombia team in Bogotá:*** the Coordinating Unit will also plan and arrange the logistics related to travel, lodging, and other issues related to the team of Stanford researchers coming annually to Bogotá.
- ***Communication strategy:*** finally, the Coordinating Unit will develop and assess the needs and efficiency of different communication strategies (social media, webpage, etc.) to make the research projects and their results available to study participants and lay public as well as experts and researchers in the field.

### B.3. Measures to Ensure Transparent, Efficient Administration to Serve All Institutions

The Coordinating Unit will take the lead on all activities to ensure a transparent and interdisciplinary collaboration between Stanford, UniAndes and the other involved institutions (IDRD, Coldeportes, etc.). As stated above, a multi-sectoral Steering Committee will be established, which will meet monthly to discuss progress, new developments, any emerging issues with standard operating procedures, and any setbacks/issues that need to be resolved. This committee will also oversee issues regarding data sharing, and

IRB related issues. Our plan is to invite all major stakeholders to designate a representative to serve on the Steering Committee, which will help facilitate efficient, transparent administration. We also believe that the in-person meetings, teleconferences, and annual meeting will enable the Coordinating Unit to ensure transparent, efficient administration. For each meeting, whether in person or by teleconference, minutes will be taken and reviewed/revised/approved at each subsequent meeting, and then posted on a study web site or portal.

Figure 1. S-C Organizational Chart

#### B.4. General Areas to be Coordinated

The Coordinating Unit will coordinate activities in the following areas. Progress in each area will be discussed at the monthly Steering Committee meetings.

- **Coordination of two pilot studies:** The Coordinating Unit will coordinate administrative activities regarding all research activities of the two pilot studies, including IRB approvals, budget administration, hiring and salary payment for personnel, monitoring progress, providing the SC with updates, and preparing progress reports. Through experience providing coordination for the pilot studies, the partnership will develop skills to support future larger-scale clinical trials and longitudinal studies.
- **Coordination of training activities:** The Coordinating Unit will administer all training activities both for the development of the proposed masters program in Epidemiology and for the professional certificate training in behavior change theories and interventions. This will include students as well as professionals in several health related professions (medical doctors, psychologists, etc.). Specifically, the Coordinating Unit will be in charge of student recruitment strategies, course evaluation, and certificates. It will maintain relations and communicate with other areas of UniAndes that are involved in the training processes (School of Medicine, School of Social Sciences, Continuing Education).
- **Coordination of the cores:** The Coordinating Unit will oversee and assist in reaching the specific aims of the cores, including budget management of core budgets, scheduling of meetings, monitoring and ordering of supplies for the cores, monitoring of core usage, management of communications within and between cores and between cores and the Planning Unit, handling communications with

investigators outside of this program who express interest in using the cores, and scheduling presentations for core leaders to present at Steering Committee meetings.

- **Oversight of database and data management:** The Coordinating Unit will develop and review relevant data sharing and data management protocols, ensuring confidentiality and care of all participant and study information. It will also assume primary responsibility for the sharing of data internally and externally in accordance with an agreed upon data sharing policy. This Unit will also oversee the informed consent process and the legal permissions needed in Colombia for storage of medical and personal information (i.e., ley habeas data).
- **Financial and grants management practices:** To facilitate the research mission, the Coordinating Unit will monitor progress and oversee expenditures on the grant, including all consultant costs, salaries, supplies, travel, etc. Project staff will assist the PIs ([name] and [name]) in preparing progress reports for the proposed project and will meet with PIs on a regular (monthly or more frequently if appropriate) basis. The project budget analyst will provide budget projections on a quarterly basis.
- **Regulatory requirements, such as IRB approvals:** The Coordinating Unit will develop the human subjects protocol and consent forms for each of the intervention projects and work with Stanford Human Subjects Administrative Panel as well as the Committee for Ethics in Research from UniAndes to maintain approval of all activities and monitor training and certification of staff. Forms will be developed, based on our extensive number of prior studies, to ensure full informed consent. IRB progress and issues will be included at each meeting of the Steering Committee.

## B.5. Needs Assessment and Community Engagement

The needs assessment will employ mixed methods and genuine community engagement to identify needs and assets as they related to PA promotion for NCD prevention. Mixed methods will include focus groups, in-depth interviews, and a social network analysis. This process will guide decision-making and strategic planning of the different actions and help identify primary gaps in advancing behavioral intervention research in Colombia and the region through a multidisciplinary approach. According to CBPR principles, community members and key stakeholders will be engaged in all phases of the research project. Using a CBPR orientation to research, the needs assessment activities in the first 3 months of the project will include significant community and stakeholder engagement that will set the stage for ongoing engagement throughout the project period and for the long-term.

[figure not shown]
**B.5.1. Qualitative methods.** We will use focus groups and in-depth interviews with community members and key stakeholders. We anticipate conducting 4 focus groups with participants and their family members from the target populations involved in the pilot studies (i.e., breast cancer patients and Ciclovías/ Recreovías participants). Additionally, we will conduct up to 3 focus groups with stakeholders from the partner organizations. Key informant interviews will be used to examine needs and assets among community members and key stakeholders that were not able to participate in the focus groups. For qualitative data, all interviews with stakeholders will be recorded and transcribed. Led by Co-Investigator [name] (see letter of support), we will use ATLAS.ti, a multifunctional software system, to code the focus group and interview transcripts. We will initially use the interview guide to organize and provide a starting list of codes related to needs and assets, which we will supplement with emergent codes to capture new factors that stem from the interview process. Two project team members will independently code the transcripts. Discrepancies in initial coding will be solved by discussion between project team members. Based on these discussions, the raters will conduct a final code of the transcripts. Intercoder agreement will be quantified for each coding domain using Cohen's Kappa:  $(\text{Observed agreement} - \text{Chance}) / (1 - \text{Chance})$ . If substantial intercoder disagreements exist, a third project team member will review the text in question to determine appropriate coding before finalizing the coding scheme.

**B.5.2. Quantitative methods.** Through network analysis, we will assess our multi-sectoral partnerships using methodology that [name] (Dual PI) has employed previously. This analysis is essential for a deeper understanding of the interconnections between groups and for revealing opportunities for partnership development. An example of such a network is provided in **Figure 2** below.

**B.5.3. Community engagement.** Investigators at both UniAndes and Stanford have extensive experience in partnering with diverse groups of community stakeholders to enhance the contextual relevance and impact of our community-based research activities. We will engage stakeholder groups to gather input on research and education priorities for the partnership. Stakeholder groups will include participants in pilot studies, multi-sectoral colleagues from the Steering Committee, and other groups as needed. The investigative team will meet with stakeholders to strategize and finalize short-, mid-, and long-term goals described in the Planning Unit description. Through applications of the Citizen Science model that Drs. [name], [name], and

[name] together have been employing in Colombia as well as with Latino populations in Mexico, Chile, and the U.S., we will collect and analyze information from residents as well as stakeholders pertaining to the programs being developed and evaluated. The *Nuestra Voz* (Our Voice) citizen science engagement model provides an evidence-based step-by-step approach for directly engaging residents from underserved communities in direct forms of neighborhood and community data collection around health issues of relevance to their community. Using a simple mobile health application, they are readily able to capture elements of their local environments that either promote or hinder PA as well as other types of health behaviors. Residents then learn how to prioritize relevant issues and communicate their findings to stakeholders in ways that promote relevant, low-cost solutions. In this model the information is evaluated by community members and subsequently presented in accessible and compelling ways to policy makers. Finally, in the last year of the project, we will hold a seminar with presentations of our Collaboratory and research projects. This seminar will have a panel including representatives of the multiple sectors (government and nongovernment) and community members representing our Collaboratory.

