3.1 Community-based intervention to promote PA among breast cancer survivors; 3.2 Longitudinal evaluation of community-wide Ciclovía/Recreovía programs.	
Short-term:
 
 
Pilot studies successfully completed
 
Manuscript describing findings submitted
 
Grant for larger scale study submitted.
 
 
Mid- & long-term:
 
 
Larger scale studies implemented
 
Behavior change (e.g., objective PA, self-report PA) documented among target populations
 
	
 
Pilot studies will be conducted by Colombian researchers with support from Stanford peers to increase research capacity
 
	
 
Dissemination of findings through multi-sectoral stakeholder partnerships will promote changes in policies to support NCD prevention practices and policies
 

Table 1 D. Performance metrics for overall aims of S-C for Aim 4: Finalize center research plans			
Performance metrics for overall aims	Expected Outcomes/ Milestones	Steps to support sustainability	How activities will inform local public policy
4.1 Needs assessment with community members and key stakeholders using focus groups, interviews and a network analysis of organizational and communication pathways and connections in Colombia	
Short-term:
 
 
3-5 focus groups and 5-8 interviews completed and analyzed
 
Network analysis completed
 
Findings summarized in scientific manuscript and in policy briefs for key stakeholders
 
 
Mid- & long-term:
 
 
Research activities aligned with needs and leverage assets
 
	
 
Methods documented to enable periodic assessment of needs and assets to account for changes in epidemiology and policy environments
 
	
 
Dissemination of findings through multi-sectoral stakeholder partnerships will promote changes in policies to support NCD prevention practices and policies
 

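### Is Cohen's kappa for the needs-assessment coding inflated because it would be computed after the two coders have discussed their discrepancies?

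*Combined protocol and SAP*

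**What the plan says.** The point arises in Section B.5.1 (Qualitative methods) of the Coordinating Unit's research strategy, which covers focus groups and interviews for the needs assessment. The steps appear in this order:

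1. Coding begins from a list based on the interview guide, "which we will supplement with emergent codes to capture new factors that stem from the interview process".
2. First pass and reconciliation: "Two project team members will independently code the transcripts. Discrepancies in initial coding will be solved by discussion between project team members".
3. Second pass and agreement: "Based on these discussions, the raters will conduct a final code of the transcripts. Intercoder agreement will be quantified for each coding domain". The statistic is Cohen's kappa, defined as observed agreement minus chance, divided by one minus chance.
4. Back-up: "If substantial intercoder disagreements exist, a third project team member will review the text in question", which happens before the coding scheme is made final.

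No other section specifies kappa. The plan sets no target or threshold for it and does not say where it will be reported. On volume, Table 1 D in Section B.6 sets a milestone of "3-5 focus groups and 5-8 interviews completed and analyzed". Section B.5.1 itself foresees 4 focus groups with participants and family members and up to 3 with stakeholders, and gives no number of interviews.

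**The concern.** Kappa is meant to show how far two people who judge separately reach the same code beyond chance. Once they have talked through their differences and coded the same transcripts again, their agreement partly reflects the conversation. The sentence on agreement comes straight after the sentence on the final code, so a literal reader would compute kappa there. The result would be too high as a measure of independent coding, and it would hide the domains that were hard to code.

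Kappa is the only reliability measure stated for this coding. The needs assessment is meant to guide the centre's planning, and Table 1 D foresees a manuscript and policy briefs from it. An inflated figure could therefore give readers more confidence in the coding than it deserves.

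**Working it through.** The plan states no kappa value, so there is no figure to reproduce. Two things can be checked: how far a post-discussion kappa could depart from an initial one, and which reading the text supports.

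**Direction and size.** From the plan's formula, κ = (Po − Pc)/(1 − Pc), so 1 − κ = (1 − Po)/(1 − Pc). If discussion removes a share r of the discrepancies and chance agreement Pc does not move, 1 − Po shrinks by the factor (1 − r), so

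κ′ = 1 − (1 − r)(1 − κ).

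With an assumed κ = 0.50:
- r = 25%: 1 − 0.75 × 0.50 = 0.625
- r = 50%: 1 − 0.50 × 0.50 = 0.75
- r = 80%: 1 − 0.20 × 0.50 = 0.90

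To let chance move, take an assumed set of 100 text segments: code applied by both 20, by coder A only 10, by coder B only 10, by neither 60. Then Po = 0.80, Pc = 0.30² + 0.70² = 0.58 and κ = 0.22/0.42 = 0.524.

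| Share of discrepancies resolved | All resolved to absent | All resolved to present |
|---|---|---|
| 25% | 0.624 | 0.658 |
| 50% | 0.733 | 0.780 |
| 80% | 0.883 | 0.915 |

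For the 50% row, resolving to absent gives 20/5/5/70, with Po = 0.90, Pc = 0.625 and κ = 0.275/0.375 = 0.733. Resolving to present gives 30/5/5/60, with Pc = 0.545 and κ = 0.355/0.455 = 0.780.

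The direction is clear in these examples. The size is not: the initial table and r are both assumptions, and the documents give neither.

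**The other direction.** The code list grows during coding. Suppose that in the first pass coder A already uses an emergent code on e segments and coder B does not yet have it. Those segments move from neither to A only.
- e = 5: 20/15/10/55, Po = 0.75, Pc = 0.35 × 0.30 + 0.65 × 0.70 = 0.56, κ = 0.19/0.44 = 0.432
- e = 10: 20/20/10/50, Po = 0.70, Pc = 0.40 × 0.30 + 0.60 × 0.70 = 0.54, κ = 0.16/0.46 = 0.348

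So an initial-pass kappa can understate the reliability of the finished codebook. Each pass answers a different question.

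**Which reading fits.**
- The re-coding sentence is tied to the discussions by its opening words. The kappa sentence has no such link and may simply name the statistic for the two-coder exercise.
- Only the first pass is described as independent.
- The final code is in the singular. If it is one agreed coding, there is no second set of codes to compare, and kappa can only use the initial pair.
- If discussion settles every discrepancy, r = 1 and κ′ = 1 in every domain (given that the code varies). Kappa would then carry no information, and the third member would have nothing to review. On the initial codings, both steps have a purpose.

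These points favour the initial codings without proving them. A second separate coding by each rater after discussion, with some disagreement left for the third member, is also consistent with the text.

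**What depends on it.** No threshold triggers an action, and review by the third member rests on an undefined notion of substantial disagreement. The final codes come from discussion and that review, whichever pass enters kappa.

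**The case for a change.** The strongest case for a change is that it costs almost nothing. On the Table 1 D counts there are 3 + 5 = 8 to 5 + 8 = 13 transcripts. Keeping two initial code files for each needs no extra coding, and one sentence would name the pass. The paragraph distinguishes an initial coding from a final code, yet the kappa sentence names neither and follows the final one. Table 1 D also wants the methods documented so that the assessment can be repeated, and a later kappa cannot be compared with this one unless the pass is known.

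Most of this stands as fact. The pass is not named, and kappa on codings revised after discussion would exceed kappa on the independent ones. What does not stand is the step to a defect. The adverse reading rests on sentence order alone, and kappa on the initial codings, which the text allows, is sound. Comparison between rounds needs only that the report says which codings were used, and that is ordinary reporting practice. Nor is the initial pass better for every purpose, as the emergent-code figures show.

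**Conclusion.** The concern does not call for a change to the plan. The text leaves open which codings enter kappa. If the post-discussion codings were used, the figure would partly measure consensus and would be too high as a statement about independent coding, by an amount that cannot be estimated here. The illustrative values, 0.52 rising to between 0.62 and 0.92, follow from the assumed table and from assuming that 25% to 80% of discrepancies are resolved.

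The gap is one that a competent qualitative analyst fills without instruction: compute kappa on the independent codings, or label a later figure as agreement after discussion. The choice is partly a trade-off between measuring independent agreement and measuring the finished codebook. The matter is confined to one descriptive reliability figure in the needs assessment. With no threshold attached, no decision is shown to turn on it, and neither the final codes nor the outcomes of the two pilot studies are affected.

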**Figure 2.**

**B.6. Evaluation, with an Emphasis on Metrics**

We have identified short- and long-term outcomes for the overall aims of the S-C (Tables 1A-D). The aims and outcomes support long-term sustainability and promote policies that support PA in Colombia.

Aims	Expected Outcomes/ Milestones	Steps to support sustainability	How activities will inform local public policy
1.1 Enhance multi-sectoral research partnerships and communication pathways for capacity building and intervention development	
Short-term:
 
 
Multi-sector partnerships are established
 
Partnerships meet at least 4 times per year
 
At least 2 partners are engaged in each of the pilot projects
 
 
Mid- & long-term:
 
 
Partners initiate their own research projects
 
	
 
Partners will be invited to 1-day courses on NCD prevention and research (see Aim 2) to increase capacity and promote sustainability
 
We will employ a CBPR approach to promote long-term engagement
 
	
 
Engaging diverse partners will inform policies for NCD prevention in various sectors
 
Training provided to partners will increase potential to infuse NCD prevention policy in all policies.
 

1.2 Finalize shared cores that will provide support for training and research activities	
Short-term:
 
 
Supportive cores are established and used by researchers in Colombia
 
 
Mid- & long-term:
 
 
All cores reside at UniAndes
 
	
 
The cores will employ capacity building strategies (e.g., co-learning) in their support to increase research capacity in all encounters
 
	
 
Cores will strengthen research capacity among Colombian colleagues for conducting research to inform policies to address NCD prevention strategies
 

Table 1 B. Performance metrics for overall aims of S-C for Aim 2: Build/expand mechanisms for capacity building in Colombia			
Performance metrics for overall aims	Expected Outcomes/ Milestones	Steps to support sustainability	How activities will inform local public policy
2.1 Scholar exchange between UniAndes and Stanford University 2.2 Professional certificate program focused on planning and evaluation of theory-based interventions for health promotion/disease prevention 2.3 Masters Program in Epidemiology with a track focused on behavioral interventions 2.4 1-day seminar courses for community members and key stakeholders	
Short-term:
 
 
At least 2 scholar exchanges have been successfully completed between Stanford and UniAndes
 
Professional certificate program is developed and delivered at least once at UniAndes
 
A behavioral science track within the epidemiology masters program is developed at UniAndes
 
At least three 1-day courses are provided to partner organizations in Colombia
 
 
Mid- & long-term:
 
 
Targeted groups (e.g., scholars, professionals, masters students) significantly increase knowledge and practices of NCD prevention research
 
	
 
Professional training activities are aimed at increasing research capacity in Colombia and the Latin American region to support long-term engagement in NCD prevention research
 
	
 
Training will focus on research aimed at sustainable policy change
 

Table 1 C. Performance metrics for overall aims of S-C for Aim 3: Conduct joint pilot projects			
Performance metrics for overall aims	Expected Outcomes/ Milestones	Steps to support sustainability	How activities will inform local public policy
3.1 Community-based intervention to promote PA among breast cancer survivors; 3.2 Longitudinal evaluation of community-wide Ciclovía/Recreovía programs.	
Short-term:
 
 
Pilot studies successfully completed
 
Manuscript describing findings submitted
 
Grant for larger scale study submitted.
 
 
Mid- & long-term:
 
 
Larger scale studies implemented
 
Behavior change (e.g., objective PA, self-report PA) documented among target populations
 
	
 
Pilot studies will be conducted by Colombian researchers with support from Stanford peers to increase research capacity
 
	
 
Dissemination of findings through multi-sectoral stakeholder partnerships will promote changes in policies to support NCD prevention practices and policies
 

Table 1 D. Performance metrics for overall aims of S-C for Aim 4: Finalize center research plans			
Performance metrics for overall aims	Expected Outcomes/ Milestones	Steps to support sustainability	How activities will inform local public policy
4.1 Needs assessment with community members and key stakeholders using focus groups, interviews and a network analysis of organizational and communication pathways and connections in Colombia	
Short-term:
 
 
3-5 focus groups and 5-8 interviews completed and analyzed
 
Network analysis completed
 
Findings summarized in scientific manuscript and in policy briefs for key stakeholders
 
 
Mid- & long-term:
 
 
Research activities aligned with needs and leverage assets
 
	
 
Methods documented to enable periodic assessment of needs and assets to account for changes in epidemiology and policy environments
 
	
 
Dissemination of findings through multi-sectoral stakeholder partnerships will promote changes in policies to support NCD prevention practices and policies
 

4.2 Finalize short-, mid-, and long-term goals and expected outcomes.	
Short-term:
 
 
Multi-sectoral partners engaged to finalize goals and outcomes
 
Goals and outcomes disseminated through policy briefs for key stakeholders
 
 
Mid- & long-term:
 
 
Goals and outcomes continuously communicated back to partners
 
	
 
CBPR approach will ensure that multiple stakeholders from various sectors are invested in the goals and outcomes to promote sustainability
 
	
 
Goals and outcomes will be focused on policy changes to sustain NCD prevention policies and outcomes
 

**B.6.1. Steps to enhance longevity of activities.** By employing a socio-ecological model and utilizing a CBPR orientation to research, all S-C priorities are designed to promote long-term sustainability of research plans, enhancement activities, and shared core facilities. The strategies for promoting long-term sustainability are provided in **Tables 1A-D**. To summarize, key strategies to promote long-term sustainability of S-C plans

include: 1) The training program we propose will help ensure longevity by training a cadre of scientists in behavioral intervention research and leaving in place courses and a Masters Program in Epidemiology; 2) We will engage the major stakeholders in this project as voting members of the Steering Committee since they represent sectors that will facilitate longevity of the program; and 3) We intend to use the pilot studies to generate preliminary results to seek major NIH grants in addition to other sources of funding to enable us to continue and enhance continuing research activities.

**B.6.2. How activities will inform local public health policy.** The strategies for informing local public health policy are provided in **Tables 1A-D**. Our primary means of informing public health policy is by engaging relevant policy making sectors to become part of our team by membership on our Steering Committee. We also plan a seminar at the end of the two years to present summary results to those groups that have the power to influence policy. Additionally, the steps to inform local public health policy in Latin America that are employed for this project will provide a road map for how this can be accomplished in other Latin American context.

